6.4 Study Intervention Compliance

The following measures will ensure that the study intervention is administered as planned (see [Table 6.1](#)), and that any non-compliance is documented so that it can be accounted for in the data analyses:

- All study interventions will be administered by qualified and trained study personnel
- The person in charge of study intervention management at the site will maintain accountability records of study intervention delivery to the study site, study intervention inventory at the site, dose(s) given to each participant, and unused or wasted doses

6.5 Dose Modification

Not applicable.

6.6 Continued Access to Study Intervention After the End of the Study

Not applicable.

6.7 Treatment of Overdose

Since the study intervention is administered by a health care professional, it is unlikely that overdose by injection occurs.

However, in the event of an overdose, the investigator should:

- 1) Contact the RMO immediately.
- 2) Evaluate the participant to determine, in consultation with the RMO, whether study intervention should be interrupted
- 3) Closely monitor the participant for any AE/SAE.
- 4) Document the quantity of the excess of the overdose in the source documents.

6.8 Concomitant Therapy

Reportable medications include medications that may affect the interpretation of safety data (eg, an antipyretic or analgesic that could have reduced the intensity or frequency of an adverse event) or may interfere with the development or measurement of the immune response (eg, the use of immune-suppressors, immune-modulators, or some antibiotics that can affect certain bioassays and intranasal and ophthalmic medications in the context of this intranasal vaccine). Some medications such as steroids can affect both the evaluation of the safety and the immune response to a vaccine.

This may include medications of interest that were started prior to the day of vaccination, and even stopped prior to enrollment if there is a reasonable possibility that they may have an impact on safety and / or immune assessment during study participation.

The following reportable medications are defined:

- Medications impacting or that may have an impact on the evaluation of the safety (eg, antipyretics, analgesics, intranasal/intraocular medications, and non-steroidal anti-inflammatory drugs [NSAIDs], systemic steroids/corticosteroids)
- Medications impacting or that may have an impact on the immune response (eg, other vaccines, blood products, antibiotic classes that may interfere with bioassays used by the Sponsor's laboratory or other testing laboratories, systemic steroids/corticosteroids, immune-suppressors, immune-modulators with immunosuppressive properties, anti-proliferative drugs such as deoxyribonucleic acid [DNA] synthesis inhibitors)
- Medications impacting or that may have an impact on both the safety and the immune response (eg, systemic steroids/corticosteroids)

Reportable medications will be collected in the CRF until the end of the unsolicited follow-up period.

Dosage and administration route, homeopathic medication, topical and inhaled steroids, as well as topical (other than intranasal and intraocular) and ear treatments will not be recorded.

Medications given in response to an AE will be captured in the “Action Taken” section of the AE CRF only. No details will be recorded in the concomitant medication Form of the CRF unless the medication(s) received belong(s) to the reportable medications list. Medications will be coded using the WHO Drug dictionary.

The following medications will be prohibited during the study period for pediatric participants: intranasal and intraocular medications, and salicylate or salicylate-containing products.

6.8.1 Rescue Medicine

Appropriate medical equipment and emergency medications, including epinephrine (1:1000), must be available at the study site in the event of an anaphylactic, vasovagal, or other immediate allergic reaction.

7 Discontinuation of Study Intervention and Participant Discontinuation/Withdrawal

Discontinuation of specific sites or of the study as a whole are detailed in [Appendix 10.1](#).

7.1 Discontinuation of Study Intervention

7.1.1 Temporary Contraindications

Should a participant experience one of the conditions listed below, the investigator will postpone further vaccination until the condition is resolved. Postponement must still be within the timeframe for vaccination indicated in the SoA.

If the postponement occurs out of the timeframe for vaccination, the participant will be permanently discontinued from study intervention but will continue to be followed for safety

TCI01: Any acute febrile illness in the past 48 hours that according to investigator judgment is significant enough to interfere with successful inoculation on the day of vaccination. A prospective participant should not be included in the study until the condition has resolved or the febrile event has subsided

TCI02: Receipt or planned receipt of any of the following vaccines prior to or after the first study intervention administration:

- any influenza vaccine within 7 days prior to and after, or
- any COVID-19 or inactivated vaccine or live-attenuated rotavirus vaccine within 14 days prior to and after, or
- any live vaccine, other than rotavirus vaccine, within 28 days prior to and after

Temporary intervention discontinuation may be considered by the investigator because of suspected AEs. For all temporary intervention discontinuations, duration should be recorded by the investigator in the source documents.

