1.3 Schedule of Activities (SoA)

Table 1.1: Schedule of activities for pediatric participants

Phase II Study, 11 Planned Visits, 2 Vaccinations, 3 Blood Samples, 9 Planned Nasal Swabs, One 6-Month Safety Follow-up Phone Call, approximately 8 Months' Duration Per Pediatric Participant

Visit/Contact*	Collection of information in the CRF	V01	V02	V03	V04	V05	V06	V07	V08	V09	V10	V11	Safety follow-up phone call	Illness Visit**
Study timelines days (D)		D01	D04	D08	D11	D15	D18	D22	D57	D64	D71	D85	D237	
Visit Interval			V01 + 3d	V01 + 7d	V01 + 10d	V01 + 14d	V01 + 17d	V01 + 21d	V01 + 56d	V08 + 7d	V08 + 14d	V08 + 28d	V08 + 6 months	
Time windows (days)		NA	[+1]	[+1]	[+1]	[+1]	[+1]	[+1]	[+7]	[+1]	[+1]	[+7]	[+14]	
Visit procedures:														
Informed consent	X	X												
Inclusion/exclusion criteria	X	X												
Collection of demographic data	X													
Collection of medical history	X Significant Medical History	X												
Physical examination	X	X							X					
Vital signs†	X	X							X					
Rapid COVID-19 test	X	X							X					

Visit/Contact*	Collection of information in the CRF	V01	V02	V03	V04	V05	V06	V07	V08	V09	V10	V11	Safety follow-up phone call	Illness Visit**
Study timelines days (D)		D01	D04	D08	D11	D15	D18	D22	D57	D64	D71	D85	D237	
Visit Interval			V01 + 3d	V01 + 7d	V01 + 10d	V01 + 14d	V01 + 17d	V01 + 21d	V01 + 56d	V08 + 7d	V08 + 14d	V08 + 28d	V08 + 6 months	
Time windows (days)		NA	[+1]	[+1]	[+1]	[+1]	[+1]	[+1]	[+7]	[+1]	[+1]	[+7]	[+14]	
Collection of reportable concomitant medications/vaccinations	X								X					X
Randomization/allocation of participant number	X	X												
Dose number	X	X							X					
Blood sampling (BL) [5 mL]	X	BL0001 Pre-vac1							BL0002 Pre-vac2			BL0003		
Nasal swab (NS)‡	X	NS0001 Pre-vac1	NS0002	NS0003	NS0004	NS0005	NS0006	NS0007		NS0008	NS0009			UN0001 to UN000X
Vaccination (vac)	X	VAC1							VAC2					
Immediate surveillance (30 min)§	X	X							X					
DC provided**		DC1							DC2					
DC reviewed††			DC1	DC1	DC1	DC1	DC1	DC1	DC1	DC2	DC2	DC2		
DC collected									DC1			DC2		
MA provided												MA		
MA reviewed												MA		
Collection of solicited administration site and systemic reactions	X	From D01 to D22							From D57 to D78					
Collection of unsolicited AEs	X	From D01 to D29							From D57 to D85					

Visit/Contact*	Collection of information in the CRF	V01	V02	V03	V04	V05	V06	V07	V08	V09	V10	V11	Safety follow-up phone call	Illness Visit†‡

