7.1.2 Definitive Contraindications

Participants will permanently discontinue (definitive discontinuation) study intervention for the reasons listed below. These participants must not receive any additional dose of study intervention but should continue to be followed for safety and immunogenicity.

Should a participant experience at least one of the conditions listed below, the investigator will discontinue vaccination:

DCI01: An anaphylactic or other significant allergic reaction to the previous dose of vaccine

DCI02: Probable or confirmed ongoing case of COVID-19 at the time of enrollment

DCI03: Serious AE assessed as related to the study vaccine following the previous dose of vaccine, based on Investigator's judgment

In the event of a local or national immunization program with a pandemic influenza vaccine or any other vaccine as needed, participants who receive pandemic influenza vaccine or any other vaccine as needed at any time during the study will not be withdrawn from the study.

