Immediate events are recorded to capture medically relevant unsolicited systemic AEs which occur within the first 30 minutes after vaccination.

Reactogenicity / Solicited Reactions:

The **reactogenicity** of a vaccine refers to the property of such vaccine to be able to produce common "expected" adverse reactions (either systemic or at the injection site) and its associated signs and symptoms.

A solicited reaction is an "expected" adverse reaction (sign or symptom) observed and reported under the conditions (nature and onset) pre-listed in the protocol and CRF (eg, nasal congestion occurring between the day of vaccination and the next 21 days).

By definition, solicited reactions are considered as being related to the corresponding IMP administered.

For injectable vaccines, solicited reactions can either be solicited injection/administration site reactions or solicited systemic reactions

Administration Site Reactions:

An injection/administration site reaction is an AR at and around the injection/administration site of the IMP. Injection/administration site reactions are commonly inflammatory reactions.

Solicited injection / administration site reactions are reactions at and around the injection / administration site of the IMP observed and reported under the conditions (nature and onset) pre-listed in the protocol and CRF. It is considered by default as being related to the IMP administered at that site.

Note: « Administration site reaction » term is only to be used for vaccines that are not intended to be administered by injection.

Systemic AR:

Systemic ARs are all ARs that are not injection or administration site reactions. They therefore include systemic manifestations such as headache, fever, as well as localized or topical manifestations that are not associated with the injection or administration site (eg, erythema that is localized but that is not occurring at the injection site).

Solicited systemic reactions are systemic AEs observed and reported under the conditions (nature and onset) pre-listed in the protocol and CRF. Solicited systemic reactions occurring

during the specified collection period are always considered related to the IMP even if there is evidence of alternative etiology.

Unsolicited AE/AR:

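### Two of the five contraindications for further vaccination (TCI02 and DCI02) cannot act at the second dose as worded, and the COVID-19 test repeated at V08 has no specific stated consequence

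*Protocol*

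**What the plan says.** Protocol Section 7.1.1 opens by saying that, when a listed condition occurs, "the investigator will postpone further vaccination until the condition is resolved". Section 7.1.2 lists conditions that end study vaccination. Since the synopsis gives doses on D01 and D57 only, both lists can govern only dose 2, at V08.

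Two of the conditions are worded as follows:

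- Temporary: "TCI02: Receipt or planned receipt of any of the following vaccines prior to or after the first study intervention administration". Three windows follow: 7 days for influenza vaccine; 14 days for COVID-19, inactivated and rotavirus vaccines; and, for the rest, "any live vaccine, other than rotavirus vaccine, within 28 days prior to and after". Exclusion E11 has the same text.
- Definitive: "DCI02: Probable or confirmed ongoing case of COVID-19 at the time of enrollment". Exclusion E05 has the same text.

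Table 1.1 (repeated as SAP Table 1.2) has a row "Rapid COVID-19 test" marked at V01 and at V08. Section 5.3 says that nothing is required beyond the exclusion criteria and the listed contraindications. Section 7.1.2 adds that a child who receives another vaccine under an immunization program is not withdrawn; it sets no spacing from dose 2.

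**The concern.** TCI02 and DCI02 read as enrollment criteria carried into a dose-2 list without a change of reference point. A site that follows the text exactly has no vaccine-spacing condition at V08. It also has a COVID-19 test result with no written rule attached. Dose 2 could then be given within days of another vaccine, or to a child who has just tested positive, without a departure from any listed condition. Different sites could also handle the same result differently.

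For the analysis, the exposure lies in what is measured after D57. Section 10.2.1 treats solicited systemic reactions in the collection period as "always considered related to the IMP even if there is evidence of alternative etiology". Fever, irritability or loss of appetite caused by another vaccine or by COVID-19 would therefore be tabulated as dose-2 reactions. Dose-2 shedding and antibody response could also be altered.

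**Working it through.** The plan states no figure on this point. The check compares the reference point of each condition with V08, and adds day arithmetic for TCI02.

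**Step 1. When dose 2 can be given.** Table 1.1 puts V08 at V01 + 56 days with a window of [+7], so D57 to D64.

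**Step 2. What each condition is measured against (Sections 7.1.1 and 7.1.2).**

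| Condition | Reference point | Can act at V08? |
|---|---|---|
| TCI01, febrile illness | Past 48 hours, day of vaccination | Yes |
| TCI02, other vaccines | First administration | No |
| DCI01, allergic reaction | Previous dose | Yes |
| DCI02, COVID-19 | Enrollment | No |
| DCI03, related SAE | Previous dose | Yes |

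Two of the five cannot act: one of two temporary and one of three definitive conditions. TCI01 also carries an enrollment sentence ("A prospective participant should not be included in the study until the condition has resolved or the febrile event has subsided"), but its operative part, "TCI01: Any acute febrile illness in the past 48 hours that according to investigator judgment is significant enough to interfere with successful inoculation", still works at V08. DCI01 and DCI03 show that the list can be written around the previous dose.

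**Step 3. TCI02 windows.** Last day of a window of w days after dose 1 = 1 + w. Gap to the opening of V08 = 57 − (1 + w). Gap to its close = 64 − (1 + w).

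- Influenza, w = 7: ends D08; gap 49 to 56 days.
- COVID-19, inactivated, rotavirus, w = 14: ends D15; gap 42 to 49 days.
- Other live, w = 28: ends D29; gap 28 to 35 days.

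The windows before dose 1 lie earlier still. None covers a vaccine given shortly before or after dose 2.

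**Step 4. DCI02.** A child who meets it at enrollment is already ineligible under E05. A correctly enrolled child cannot newly meet it at V08.

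**Step 5. The V08 test.** The only rules that turn on having COVID-19 are E05 and DCI02, and both look at enrollment. No section says what follows a positive result at V08.

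**Step 6. Which results are exposed.**

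- Dose-2 solicited reactions (D57 to D78) and dose-2 unsolicited AEs, AESIs and MAAEs (D57 to D85), on the SafAS.
- D64 and D71 swabs: the dose-2 part of the primary shedding endpoint, and secondary transmission, both on the SafAS (SAP 3.4.2.2 and 3.4.3.3).
- D85 titers, on the FAS.

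Not exposed: primary transmission (D01 to D22) and PPAS membership, whose criteria concern eligibility, the D01 dose and the period to D22.

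**The case against.** **Other written routes exist.** This stands. Section 7.1.3 lets the investigator stop study intervention for safety. Section 7.1.1 allows temporary discontinuation for suspected AEs. The opening of Section 8 requires immediate safety concerns to be discussed with the sponsor. TCI01 covers a child with significant fever. A reader might infer that nothing can be done at V08, or that the whole contraindication list fails; the documents support neither. What is missing is a rule specific to COVID-19 and to nearby vaccines.

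**The attribution convention applies to both arms.** This also stands. Allocation is 1:1, randomized and observer-blind, so nearby vaccines and COVID-19 add background to both groups. A reader might infer a biased vaccine-placebo contrast; the documents show no differential effect. The exposure is to the rates described within each arm. COVID-19 caught after dose 2 would be counted under any V08 rule, and illness swabs may be tested for it.

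**The vaccine windows and the postponement limit.** A reader might infer that 14- and 28-day windows cannot fit a 7-day postponement. They can, because only the days left to run count. If the listed windows were applied to dose 2, purely for illustration, a 28-day window from D36 ends at 36 + 28 = D64, a 14-day window from D50 at 50 + 14 = D64, and a 7-day window from D57 at 57 + 7 = D64. Section 7.1.1 also says what happens beyond the limit: study vaccination stops and safety follow-up continues. There is no error there.

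**The SafAS clause on vaccines outside the protocol design.** It sets aside safety data recorded for such a vaccine. It does not say that diary data after a study dose are removed because another vaccine was given nearby.

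**Conclusion.** The point holds for TCI02, DCI02 and the V08 test. These are stated rules that cannot operate at the only visit they could govern. Followed exactly, the text leaves dose 2 next to another vaccine, or with a positive test, to TCI01 and general discretion.

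The wording reaches all 100 planned children, but that is not the number affected: the documents give no rate of other vaccination or of COVID-19 around D57, so the effect on any estimate cannot be sized. That another vaccine or COVID-19 would change shedding or titers is an assumption; that it would enter the solicited reaction counts follows from the protocol's own convention.

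All analyses are descriptive, and primary transmission is untouched. This is a safety-relevant wording correction that should be made, and it ranks below defects that threaten the main result.

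**What to change.** Reconcile Protocol Sections 7.1.1 and 7.1.2 with E05, E11 and the V08 column of Table 1.1:

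- State, for TCI02 and for DCI02, the administration or visit against which each is measured when dose 2 is considered.
- State the consequence of the V08 rapid COVID-19 test.

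The content of both rules is for the sponsor's clinical team. The cost is wording at the next amendment and a letter to sites.

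Optionally, add to the SAP a flag for dose-2 records with another vaccine inside the listed windows, and show dose-2 safety with and without them. Section 6.8 already makes other vaccines reportable, and Table 1.1 collects them at V08, so no new data item is needed. Confirm that the form captures vaccines given between D29 and D57: the dose-1 unsolicited period ends on D29, and a 28-day look-back from D57 starts at 57 − 28 = D29.

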7.1.2 Definitive Contraindications

Participants will permanently discontinue (definitive discontinuation) study intervention for the reasons listed below. These participants must not receive any additional dose of study intervention but should continue to be followed for safety and immunogenicity.

Should a participant experience at least one of the conditions listed below, the investigator will discontinue vaccination:

DCI01: An anaphylactic or other significant allergic reaction to the previous dose of vaccine

DCI02: Probable or confirmed ongoing case of COVID-19 at the time of enrollment

DCI03: Serious AE assessed as related to the study vaccine following the previous dose of vaccine, based on Investigator's judgment

In the event of a local or national immunization program with a pandemic influenza vaccine or any other vaccine as needed, participants who receive pandemic influenza vaccine or any other vaccine as needed at any time during the study will not be withdrawn from the study.

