5.2 Exclusion Criteria

Pediatric participants are not eligible for the study if any of the following criteria are met:

MEDICAL CONDITIONS

- E01.** Known or suspected congenital or acquired immunodeficiency; or receipt of immunosuppressive therapy, such as anti-cancer chemotherapy or radiation therapy, within the preceding 6 months; or long-term systemic corticosteroid therapy (prednisone or equivalent for more than 2 consecutive weeks within the past 3 months)
- E02.** Known systemic hypersensitivity to any of the study intervention components, or history of a life-threatening reaction to the study intervention used in the study or to a product containing any of the same substances²
- E03.** Chronic illness that, in the opinion of the investigator, is at a stage where it might interfere with study conduct or completion³
- E04.** Any acute febrile illness in the past 48 hours that according to investigator judgment is significant enough to interfere with successful inoculation on the day of vaccination. A prospective participant should not be included in the study until the condition has resolved or the febrile event has subsided.
- E05.** Probable or confirmed ongoing case of COVID-19 at the time of enrollment
- E06.** Member of a household that contains an immunocompromised individual, including, but not limited to:
 - a person who is HIV infected
 - a person who has received chemotherapy within the 12 months prior to study enrollment
 - a person who has received (within the past 6 months) or is receiving (at the time of enrollment) immunosuppressant agents
 - a person living with a solid organ or bone marrow transplant
- E07.** Member of a household that includes, or will include, an infant who is less than 6 months of age at the time of enrollment

² The components of study intervention are listed in Section 6.1 of the protocol and in the Investigator's Brochure.

³ Chronic illness may include, but is not limited to, cardiac disorders, lung disease (including any history of reactive airway disease, receipt of bronchodilator or inhaled steroid therapy, or medically diagnosed wheezing), atopy, renal disorders, auto-immune disorders, diabetes, psychomotor diseases, and known congenital or genetic diseases

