E08. Attends a daycare facility and shares a daycare room with infants less than 6 months of age, and parent/legally acceptable representative is unable or unwilling to suspend attendance at the daycare facility for 28 days following study intervention administration

E09. Any need of supplemental oxygen therapy in a home or hospital setting at the time of enrollment.

PRIOR/CONCOMITANT THERAPY

E10. Participant's mother previous receipt or planned administration of an investigational RSV vaccine or any monoclonal antibody (such as Infliximab) during pregnancy and/or breastfeeding.

E11. Receipt or planned receipt of any of the following vaccines prior to or after the first study intervention administration:

- any influenza vaccine within 7 days prior to and after, or
- any COVID-19 or inactivated vaccine or live-attenuated rotavirus vaccine within 14 days prior to and after, or
- any live vaccine, other than rotavirus vaccine, within 28 days prior to and after

E12. Previous receipt of an investigational RSV vaccine or receiving any anti-RSV product (such as ribavirin or RSV IG or RSV monoclonal antibody) at the time of enrollment.

E13. Receipt of immune globulins, blood or blood-derived products in the past 3 months

E14. Receipt of intranasal and intra-ocular medications within 3 days prior to study enrollment

E15. Receipt at the time of enrollment or previous receipt of salicylate (aspirin) or salicylate-containing products

PRIOR/CONCURRENT CLINICAL STUDY EXPERIENCE

E16. Participation at the time of study enrollment (or in the 6 weeks preceding the first study intervention administration) or planned participation during the present study period in another clinical study investigating a vaccine, drug, medical device, or medical procedure

OTHER EXCLUSIONS

E17. Deprived of freedom in an emergency setting, or hospitalized involuntarily

E18. Identified as a natural or adopted child of the Investigator or employee with direct involvement in the proposed study

If the participant has a primary physician who is not the investigator, the site should contact this physician with the participant's consent to inform him / her of the participant's participation in the study. In addition, the site should ask this primary physician to verify exclusion criteria relating to previous therapies, such as receipt of blood products or previous vaccines.

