5.3 Lifestyle Considerations

No other restrictions than the ones listed in the exclusion criteria or in the contraindications for subsequent vaccinations are required.

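### Cheap improvement: in the visible protocol and SAP, no scheduled step re-checks contact-protection criteria E06-E08 before the second live-virus dose at V08

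*Protocol*

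**What the plan says.** **Entry criteria (Protocol 5.2).** E06 excludes children whose household contains an immunocompromised person. One of its four examples reads "a person who has received (within the past 6 months) or is receiving (at the time of enrollment) immunosuppressant agents". E07 excludes a "Member of a household that includes, or will include, an infant who is less than 6 months of age at the time of enrollment". E08 concerns a child who shares a daycare room with infants under 6 months and whose parent is "unable or unwilling to suspend attendance at the daycare facility for 28 days following study intervention administration".

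**Schedule (Protocol Table 1.1, repeated in SAP Table 1.2).** The row "Inclusion/exclusion criteria" is marked at V01 only. Physical examination, vital signs and the rapid COVID-19 test are marked at V01 and again at V08, the dose 2 visit.

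**Rules before dose 2 (Protocol 7.1).** TCI01 is acute febrile illness and TCI02 is receipt of other vaccines. For these, 7.1.1 adds: "Postponement must still be within the timeframe for vaccination indicated in the SoA". If that window is missed, dosing stops permanently. Section 7.1.2 says "Should a participant experience at least one of the conditions listed below, the investigator will discontinue vaccination" and lists allergic reaction (DCI01), COVID-19 (DCI02) and related SAE (DCI03).

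**Between doses (Protocol 5.3).** "No other restrictions than the ones listed in the exclusion criteria or in the contraindications for subsequent vaccinations are required".

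**The concern.** E06 to E08 protect third parties rather than the vaccinee. Most of those people have not consented to anything in this study. The trial exists because transmissibility is not yet established, and section 4.1 says that it recruits where transmission is most likely. Virus is given twice, but the contact situation is asked about once.

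A site that follows the written plan exactly could give live virus at D57-D64 to a child whose household or daycare room has, since V01, gained someone these criteria are meant to protect. Section 4.2 expects less shedding after dose 2, which limits the risk but does not remove it. Section 4.3 says that, for other attenuated RSV and PIV3 candidates, repeat doses mainly infected children who had not responded to the first. By analogy, some children here may have their first productive infection after D57.

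**Working it through.** The plan gives no figure on this point to reproduce. The check sets the rules side by side, then does the dates and the cost.

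**1. Which entry criteria have a counterpart at dose 2**

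| Entry criterion | Counterpart in 7.1 |
|---|---|
| E04 febrile illness | TCI01 |
| E11 other vaccines | TCI02, but with E11's wording, which names the first dose: "Receipt or planned receipt of any of the following vaccines prior to or after the first study intervention administration" |
| E05 COVID-19 | DCI02, but still tied to enrollment |
| E06, E07, E08 contacts | none |

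Read literally, TCI02 and DCI02 do not reach dose 2 either. Their place among the contraindications to further vaccination, and the COVID-19 test at V08, show that they are meant to.

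**2. What each contact criterion leaves open**

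- E06: the chemotherapy and immunosuppressant examples are anchored to enrollment. The stem and the HIV and transplant examples carry no date. Nothing in it looks forward, so a household member who becomes immunocompromised after V01 is not caught. This is the clearest gap.
- E07: its forward-looking clause covers births and arrivals that can be foreseen at V01. Only an unforeseen arrival is missed.
- E08: unlike E11, it is not limited to the first administration, so the 28-day suspension can be read as applying after each dose. It binds only families whose child already shares such a room when screened. A room that later takes in young infants is missed.

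**3. Age of the contact check**

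- Dose 2: V01 + 56 days, window +7, so 56 to 56 + 7 = 63 days after the check (D57-D64).
- End of the 28 days after dose 2: 56 + 28 = 84 to 63 + 28 = 91 days (D85-D92).

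**4. How many births E07 already handles**

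Assume delivery at 37 weeks (259 days) or, at the extreme, 27 weeks (189 days), the gestational limits in I03. Minimum gestation at V01 for a birth by the end of the period:

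- 37 weeks: 259 - 91 = 168 days (24 weeks) to 259 - 84 = 175 days (25 weeks).
- 27 weeks: 189 - 91 = 98 days (14 weeks) to 189 - 84 = 105 days (15 weeks).

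Earlier births imply a more advanced pregnancy at V01. Most births in the window are therefore foreseeable at V01 and fall under E07.

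**5. Cost of losing second doses**

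With zero detections among n placebo recipients at D64/D71, the Clopper-Pearson two-sided 95% upper limit is 1 - 0.025^(1/n):

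- n = 50 (planned): 7.11%
- n = 49 (one pair withheld, one of the two on placebo): 7.25%
- n = 45 (five placebo recipients lost): 7.87%

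**The case against.** The strongest reply is that little remains and that other safeguards exist. E07 and E08 already do much of the work. The investigator may stop dosing for safety (7.1.3), the sponsor may delay it (5.5), the internal safety committee may recommend a pause (10.1.5), and section 8 requires immediate safety concerns to be raised with the sponsor. Sites see families at seven visits from D01 to D22, some possibly at home or at the daycare center, and the child is examined at V08. Close contacts with respiratory illness are followed for 28 days after any dose.

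Much of this stands, and it keeps the severity low. It does not close the gap. The discretionary powers work only if someone already knows of the new contact, and no scheduled step asks. Illness visits act after symptoms. An investigator could sensibly re-apply E06-E08 at V08, but nothing in the visible text says to.

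Some further inferences are tempting but unsupported:

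- A reader might infer that none of E06-E08 reaches dose 2. E07's forward-looking clause and E08's unrestricted 28 days say otherwise, and only two of E06's four examples are date-bound.
- A reader might infer that placebo allocation halves the risk. Randomization is 1:1 and stratified by contact group, so an enrolled household will usually contain a vaccinee.
- A reader might turn the 15 infants aged 4 to 6 months in section 2.2 into an upper limit on risk. The text does not say that all 15 were vaccinated, absence of safety signals is not a zero count, and direct dosing is not exposure of a contact.

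**Conclusion.** The point holds as a low-severity safety improvement, with medium confidence. In the visible protocol and SAP, the only scheduled contact check is 56 to 63 days old at dose 2 and 84 to 91 days old when the following 28 days end. No listed contraindication concerns contacts. Three situations are uncovered: household immunosuppression that begins after V01, a newly shared daycare room, and an unforeseen household infant.

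The documents give no frequency for these changes and none is assumed, so the number of contacts at risk cannot be stated. A reader might conclude that sites have no instruction at all on this matter. The documents do not support that, because the consent pages and the Investigator's Brochure were not available and may contain one. Even so, a rule on when to withhold a dose belongs in section 7.1. No estimate or analysis in the plan is wrong because of this gap.

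**What to change.** 1. Add one household and daycare contact question, covering E06-E08, to the V08 column of Table 1.1 and SAP Table 1.2.
2. Add a temporary contraindication to 7.1.1: the child now shares a daycare room with infants under 6 months. It is resolved if attendance is suspended for 28 days after dose 2; otherwise dosing is discontinued once the +7 day window passes.
3. Add a definitive contraindication to 7.1.2: the household now includes an immunocompromised person or an infant under 6 months.
4. Apply both to both arms, since sites are blinded, and follow these children for safety and immunogenicity. Section 7.1.2 already says so; 7.1.1 mentions safety only and needs the addition.
5. Reword TCI02 and DCI02 to refer to each dose, not to the first administration or enrollment.

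**Cost.** An occasional second dose is lost, possibly for every enrolled child in a household; one pair is 2 of 100 participants. Their D64/D71 data go with it. Those data are part of the primary shedding endpoint and all of the secondary transmission endpoint, but the loss of precision worked out above is small. D85 blood would reflect one dose. A child kept out of daycare says little about daycare transmission at D64/D71. The D01-D22 transmission endpoint is unaffected. So is the PPAS, provided the new rules are written as contraindications and not as entry criteria, because its other exclusions concern D01 and the period to D22.
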